Study Population & Planned Sample Size	Cases: 500 PLWHIV with COVID-19 Controls: 1,000 PLWHIV without COVID-19 & upto 1500 HIV seronegative COVID-19 patients
Eligibility Criteria	Cases: at least 18 years of age with documented HIV-1 infection and confirmed SARS-CoV-2 infection by documented, or patient-reported, positive result on PCR testing of a nasopharyngeal or respiratory sample, before 1 st April 2021. Controls: at least 18 years of age with either: documented HIV-1 infection; or confirmed SARS-CoV-2 infection by documented, or patient-reported, positive result on PCR testing of a nasopharyngeal or respiratory sample, before 1 st April 2021. Controls must also meet the matching criteria.
Indication	HIV & COVID-19
Methodology	Only real-world retrospective data will be used for this study. Deidentified retrospective data will be transcribed into the eCRF system from source data at each clinical site or from existing COVID-19 cohort databases, where appropriate. No personal identifiable data will be transmitted to NEAT ID. Each case will be matched to control as per the criteria set out below: For comparing PLWHIV & COVID-19 versus HIV seronegative COVID-19 patients, a 1:1 or 1:3 matching will be performed according to the following criteria: 
• Age (+/- 5 years)• Sex• Ethnicity (where available)• Month of COVID-19 diagnosis (+/- 2 months)• COVID-19 diagnosis inpatient, 1:1 matching OR• COVID-19 diagnosis outpatient (ambulatory), 1:3 matching For comparing PLWHIV & COVID-19 versus PLWHIV without COVID-19, a 1:2 matching for similar risk of acquiring COVID-19 will be performed according to the following criteria: 
• Age (+/- 5 years)• Sex• Ethnicity (where available)
Number of sites	Up to 30 sites

Objectives	
Primary
 
 1. To describe outcomes of COVID-19 in PLWHIV in comparison to HIV seronegative COVID-19 controls. 2. To identify risk factors (e.g. CD4 cell nadir, current CD4 count, comorbidities) for severe COVID-19 outcomes within the group of PLWHIV. 	
Secondary
 
 1. To describe differences in the clinical manifestation of COVID-19 in PLWHIV as compared to HIV seronegative controls. 2. To describe the response to treatment, including supportive care and novel therapeutics against COVID-19, including antiviral or immunomodulatory therapy 3. To describe the co-morbidities in PLWHIV and controls with COVID-19 4. To compare the COVID-19 severity in PLWHIV and controls at diagnosis and hospital admission.
Outcome Measures	
Primary
 
 1. The primary endpoint is a composite of: Critical care admission (high dependency unit or intensive care unit), mortality in hospital or palliative discharge when discharged from hospital, or mortality at 6 weeks after diagnosis of COVID-19 or at discharge from hospital (where applicable) 	
Secondary
 
 1. Hospitalisation for COVID-19 2. Length of stay in hospital 3. Length of stay on ICU 4. Number of ventilator-free days (VFDs) 5. Length of extracorporeal membrane oxygenation (ECMO) 6. Need for kidney replacement therapy 7. Measurement of total comorbidity burden using the Charlson Comorbidity Index (CCI) and age-adjusted CCI (ACCI) 8. Estimate risk of 30-day mortality after COVID-19 infection using pre-COVID health status (estimated using the Veterans Health Administration COVID-19 (VACO) index) 9. Inflammatory marker and blood cell counts at COVID-19 diagnosis

FUNDING AND SUPPORT

FUNDER(S)

Gilead Sciences, Inc.

[name]

[name]

NEAT ID Foundation (NEAT ID)

Registered address: [name]

Administrative office: [name]

COLLABORATORS/KEY CONTRIBUTORS

Research Organisation King's Cross (KC) Ltd.

[name]

[name]

NEAT ID Foundation (NEAT ID)

Registered address: [name]

Administrative office: [name]

[name]

Inserm and Sorbonne University

[name]

LIST OF ABBREVIATIONS

Acronym	Description
ACCI	Age-adjusted Charlson Comorbidity Index
ART	Antiretroviral Therapy/Treatment
ARV	Antiretroviral
CCI	Charlson Comorbidity Index
CI	Chief Investigator
CRF	Case Report Form
CRO	Contract Research Organisation
CTA	Clinical Trial Authorisation
EC	European Commission
ECMO	Extracorporeal Membrane Oxygenation
eCRF	Electronic Case Report Form
EMEA	European Medicines Agency
EU	European Union
EUCTD	European Clinical Trials Directive
GDPR	General Data Protection Regulation
GCP	Good Clinical Practice
GPP	Good Pharmacoepidemiology Practice
HIV	Human Immunodeficiency Virus
ICH	International Conference on Harmonisation of technical requirements for registration of pharmaceuticals for human use.
ISF	Investigator Site File
ISPE	International Society for Pharmacoepidemiology
MS	Member State
R&D	Research & Development
PI	Principal Investigator
PLWHIV	People Living With HIV
REC	Research Ethics Committee
SOP	Standard Operating Procedure
TMF	Trial Master File
VACO	Veterans Health Administration COVID-19
VFD(s)	Ventilator-Free Day(s)

1. BACKGROUND

COVID-19 is a public health emergency of international concern with mortality rates of 2-4% and highest death risk in elderly male patients and those with co-morbidities. Little is known about the disease course of COVID-19 in specific patient groups with immunosuppression or people living with HIV (PLWHIV) [1-5] and whether PLWHIV may have some degree of protection due to their ART compounds [6-9]. Irrespective of their antiretroviral therapy, PLWHIV with co-morbidities are expected to accumulate risk factors for COVID-19. Also, incomplete immune reconstitution may put them at risk for severe COVID-19.

2. RATIONALE

Current evidence indicates that the risk of severe COVID-19 illness increases with age, male gender and with certain chronic medical problems such as arterial hypertension, cardiovascular disease, chronic lung disease, obesity and diabetes. Whether or not PLWHIV on treatment with a normal CD4 cell count and suppressed HIV-RNA are at an increased risk of serious illness or death, many will have other conditions that increase their risk. Indeed, almost half PLWH in Europe are older than 50 years and chronic medical conditions, including cardiovascular and chronic lung disease, are more common in PLWHIV.

Case series of PLWHIV with COVID-19 from China, Spain, Germany, Italy and the United States [10-22] show no clear evidence for a higher COVID-19 infection rate or different disease course in people with and without HIV. Of note, most case series of PLWHIV report a younger age in their study population than in HIV-negative hospitalised COVID-19 patients, but comparable rates of comorbidities. A cohort study from the United Kingdom reported a small potential increase in the risk of mortality among PLWHIV once hospitalised with COVID-19, albeit with no data around the risk of developing severe COVID-19 or hospitalisation among this cohort in the first place and no data on antiretroviral therapy (ART), viral load (VL) or CD4 count [23].

An analysis of risk factors for COVID-19 deaths in the Western Cape [24] described after adjusting for other risk factors that HIV increased a COVID-19 patient's death risk by a factor of 2.14 (95% CI 1.70;2.70), and active TB by a factor of 2.70 (95% CI 1.91-4.04). Finally, Spanish researchers described the incidence of COVID-19 and risk of hospitalization among 77,590 PLWHIV receiving ART [7]. During a 3-month period, 236 PLWHIV were diagnosed with COVID-19, and 151 were hospitalized. The risk of hospitalization by NRTI treatment per 10,000 persons was lowest for TDF/FTC (10.5), while other NRTI strategies were similar.

Data regarding the activity of TDF against SARS CoV-2 is conflicting. In Silico data suggests that TDF/FTC may bind to SARS CoV-2 Nsp1 protein [25], an unreviewed study shows that TDF and TAF may inhibit the SARS-CoV-2 polymerase [26], one in vitro study supports antiviral activity of TDF/FTC [27] and an animal models suggest shortened duration of symptoms, and possibly infectiousness [28]. However, two studies have failed to demonstrate any in vitro activity of tenofovir against CoV-2 [29,30]. There is ongoing discussion and research around other antiretrovirals, which may have some activity against COVID-19. The first randomised clinical trial (RCT) with lopinavir-ritonavir (LPV/r) demonstrated no benefit over standard care in 199 hospitalised adults with severe COVID-19 [31]. Since then the large UK RECOVERY trial, which to date has randomised almost 12,000 people hospitalised with COVID-19 to different therapeutic options, has stopped recruitment to the LPV/r arm after a review by Data Monitoring Committee revealed no benefit of LPV/r over standard of care in terms of mortality, ventilation requirement or length of stay [32]. Moreover, an Italian case series suggests boosted DRV

does not prevent SARS-CoV-2 infection in PLWHIV or protect against worsening respiratory function [33].

Rapid data collection and analysis about COVID-19 in PLWHIV will depend on international multi-centre collaborations, for which NEAT ID has a strong expertise. The majority of PLWHIV in Europe are in routine clinical care, allowing for a comprehensive data collection about COVID-19 and studying the impact of HIV drugs and specific risk factors. The NEAT ID COVID-19 Coinfection Dashboard was established in March 2020 to collect data on the number of PLWHIV co-infected with COVID-19 in Europe and has provided evidence that a significant number of PLWHIV are suffering from COVID-19 in Europe already and that these individuals can be enrolled into an Epidemiology and Real-World-Data study.

There are two central questions to address:

1. Is there a particular risk for COVID-19 in PLWHIV as compared to HIV seronegative control COVID-19 cases?
2. Are there particular factors, within the group of PLWHIV, which put them at risk for a more severe COVID-19 disease course?

3. OBJECTIVES AND OUTCOME MEASURES/ENDPOINTS

It is hypothesised that HIV infection is a risk factor for more severe COVID-19 outcomes and that advanced immunodeficiency as defined by current CD4 T-cell count or CD4 T-cell nadir is a risk factor for more severe COVID-19 outcomes in PLWHIV.

3.1 Primary objective

1. To describe outcomes of COVID-19 in PLWHIV in comparison to HIV seronegative COVID-19 controls.
2. To identify risk factors (e.g. CD4 cell nadir, current CD4 count, co-morbidities) for severe COVID-19 outcomes within the group of PLWHIV.

3.2 Secondary objectives

1. To describe differences in the clinical manifestation of COVID-19 in PLWHIV as compared to HIV seronegative controls.
2. Describe, where appropriate, the response to treatment, including supportive care and novel therapeutics against COVID-19, including antiviral and immunomodulatory therapies
3. To describe the co-morbidities in PLWHIV and controls with COVID-19
4. To compare the COVID-19 severity in PLWHIV and controls at diagnosis and hospital admission.

3.3 Primary endpoint/outcome

1. The primary endpoint is a composite of: Critical care admission (high dependency unit or intensive care unit), mortality in hospital or palliative discharge when discharged from hospital, or mortality at 6 weeks after diagnosis of COVID-19 or at discharge from hospital (where applicable)

3.4 Secondary endpoints/outcomes

1. Hospitalisation for COVID-19
2. Length of stay in hospital
3. Length of stay on ICU
4. Number of ventilator-free days (VFDs)
5. Length of extracorporeal membrane oxygenation (ECMO)
6. Need for kidney replacement therapy
7. Measurement of total comorbidity burden using the Charlson Comorbidity Index (CCI) and age-adjusted CCI (ACCI)
8. Estimate risk of 30-day mortality after COVID-19 infection using pre-COVID health status (estimated using the Veterans Health Administration COVID-19 (VACO) index)
9. Inflammatory marker and blood cell counts at COVID-19 diagnosis

4 STUDY DESIGN

This is an observational, retrospective, case-control study.

4.1 Study Schema

[figure not shown]

Figure 1: Study design with cases (PLWHIV & COVID-19) and two matched control groups.

In total, 500 cases and up to 2500 controls will be analysed.

Only real-world retrospective data will be used for this study. Deidentified retrospective data will be transcribed into the eCRF system from source data at each clinical site or from existing COVID-19 cohort databases, where appropriate.

For comparing PLWHIV & COVID-19 versus HIV seronegative COVID-19 patients, a 1:1 and 1:3 matching will be performed according to the following criteria:

- Age (+/- 5 years)
- Sex
- Ethnicity (where available)
- Month of COVID-19 diagnosis (+/- 2 months)
- COVID-19 diagnosis inpatient, 1:1 matching
OR
- COVID-19 diagnosis outpatient (ambulatory), 1:3 matching

For comparing PLWHIV & COVID-19 versus PLWHIV without COVID-19, a 1:2 matching for similar risk of acquiring COVID-19 will be performed according to the following criteria:

- Age (+/- 5 years)
- Sex
- Ethnicity (where available)

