6.2 Data collection

Only real-world retrospective data will be used for this study. Deidentified retrospective data will be transcribed into the eCRF system from source data at each clinical site or from existing COVID-19 cohort databases, where appropriate. No personal identifiable data will be transmitted to NEAT ID. The data elements will be transcribed from source data according to the data collection list below. Mechanisms to ensure data quality and integrity will be deployed as per applicable standard operating procedures and in line with GCP and GPP. Patients and controls will be identified and documented by participating sites, provided unbiased matching for inpatient/outpatient status at the time of COVID-19 diagnosis is ensured. Alternatively, and to avoid potential site-related bias during selection of HIV negative controls with COVID-19 diagnosed in hospital, data from matched controls will be obtained from appropriate existing COVID-19 cohort databases, e.g. LEOSS (Lean European Open Survey on SARS-CoV-2 infected patients) or ISARIC (International Severe Acute Respiratory and emerging Infection Consortium).

For all patients the following information will be collected:

- Age
- Sex
- Ethnicity (where available)
- Comorbidities (see appendix 1)
- Weight (kg) and height (m) (to calculate BMI)

For patients with COVID-19 the following information will be collected (where applicable):

- Date of positive PCR test result (documented or patient-reported)
- COVID-19 diagnosis inpatient or outpatient
- All-cause mortality in hospital, or palliative discharge, or mortality at 6 weeks after diagnosis of COVID-19 or at discharge from hospital
- Hospitalisation for COVID-19 and length of hospitalisation
- Critical care admission (high dependency unit or intensive care unit) for COVID-19 and length of stay in critical care
- Length of invasive ventilation
- Length of extracorporeal membrane oxygenation (ECMO)
- Need for kidney replacement therapy
- Inflammatory markers and blood cell counts at COVID-19 diagnosis¹ (if available):
 - Full blood cell count (Platelet count, RBC Count, WBC count (absolute), Haemoglobin, Haematocrit, MCV, MCH, Neutrophils, Lymphocytes, Monocytes, Eosinophils, and Basophils), ALT, AST, total bilirubin, urea, serum creatinine, calcium, glucose and HbA1C levels, total cholesterol, triglycerides, CRP, D-dimer, ferritin, and lactate dehydrogenase

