7.3.2 Primary outcome analysis

The first primary outcome analysis will be performed on PLWHIV with COVID-19 versus HIV uninfected individuals with COVID-19. The endpoint is the occurrence of critical care admission (high dependency unit or intensive care unit), mortality in hospital or palliative discharge when discharged from hospital, or mortality at 6 weeks after diagnosis of COVID-19 or at discharge from hospital (where applicable). Kaplan-Meier estimates will be used to estimate the proportion of participants with the primary endpoint events. Unadjusted and adjusted hazard ratios (HR) will be estimated using the Cox proportional hazard model to assess the impact of HIV-infection on the severity of COVID-19. The validity of the proportionality assumption will be assessed and tested. The adjusted variables will be the following (potential confounders): Age (<60 vs 60-64 vs 65-69 vs 70-74 vs ≥75 years); Sex at birth (female vs male); Obesity (BMI>30 kg/m²); and Comorbidities (see appendix 1).

The second primary outcome analysis will be performed within the group of PLWHIV (PLWHIV with COVID-19 versus PLWHIV without COVID-19). The endpoint is to assess factors associated with severe COVID-19 within the group of PLWHIV. Conditional logistic regression models will be used to account for the case-control matching. The following variables will be assessed: Age (<60 vs 60-64 vs 65-69 vs 70-74 vs ≥75 years); Sex at birth (female vs male); Obesity (BMI >30 kg/m²); Comorbidities (see appendix 1); time since HIV diagnosis (years); current ART; CDC disease stage; CD4 cell nadir; last CD4 cell count/HIV-RNA before COVID-19 diagnosis (including CD4% and CD4/CD8 ratio) at baseline. For continuous variables, the decision to treat the variable as a continuous or categorical variable (as tertile) will be based on the lowest Akaike information criterion value for the corresponding univariable conditional logistic regression analysis. Variables achieving P < 0.20 in the univariable analysis will be retained for the multivariable analysis.

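### Matching HIV-negative controls on inpatient or outpatient status at diagnosis limits the primary hazard ratio to an effect given setting; the planned unstratified Cox model does not deliver even that, yet it is read as the impact of HIV on severity

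*Combined protocol and SAP*

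**What the plan says.** Section 4.1 and the synopsis match HIV-negative COVID-19 controls to cases on age, sex, ethnicity where available, month of diagnosis and setting at diagnosis. The control ratio depends on setting: "COVID-19 diagnosis inpatient, 1:1 matching" or "COVID-19 diagnosis outpatient (ambulatory), 1:3 matching". Section 5.1 makes meeting the matching criteria a condition of inclusion for controls. Section 6.2 fixes the time point and allows sites to supply controls "provided unbiased matching for inpatient/outpatient status at the time of COVID-19 diagnosis is ensured". It offers cohort databases as an alternative source "to avoid potential site-related bias during selection of HIV negative controls with COVID-19 diagnosed in hospital".

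Section 3 sets the hypothesis: "It is hypothesised that HIV infection is a risk factor for more severe COVID-19 outcomes". Section 3.3 defines the endpoint: "The primary endpoint is a composite of: Critical care admission (high dependency unit or intensive care unit), mortality in hospital or palliative discharge", together with death by six weeks or at discharge. Section 7.3 asks whether HIV is associated with severe COVID-19. Section 7.3.2 fits a Cox model "to assess the impact of HIV-infection on the severity of COVID-19", adjusted for age, sex, obesity and comorbidities. It names no term for setting and no stratification by setting or matched set. No section limits the HR to an effect given setting at diagnosis.

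**The concern.** HIV infection normally precedes the setting in which COVID-19 is diagnosed, and sicker people are more likely to be diagnosed in hospital. Because each control takes the setting of its case, the cases determine the inpatient share among controls. The study then cannot learn whether HIV makes inpatient diagnosis more likely, and no analysis of the matched sample alone can recover that part of an effect on critical care or death.

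Two consequences follow for the first primary objective:

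- **Interpretation.** Even a correct matched analysis estimates severity after diagnosis, given setting. Sections 3, 7.3 and 7.3.2 frame the result more broadly.
- **Analysis.** Pooling 1:1 and 1:3 sets in one unstratified model compares cases with controls who include proportionally fewer inpatients. If inpatients have the higher event risk, the HR is pushed above 1 whether or not HIV matters.

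In addition, if clinicians admit people with HIV at a lower threshold, the comparison within each setting can be biased even when the analysis is properly stratified.

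**Working it through.** The plan gives no figure on this point. Its related calculation, Table 1 in section 7.1, reproduces with Freedman's log-rank formula (500 cases, 1,500 controls): 90.8, 81.2, 86.2 and 85.4% against the stated 90, 81, 86 and 85%. That table is not in dispute. It supplies a yardstick: the study is powered for HRs of 1.3 to 1.6.

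**Inputs from the documents.** Ratios 1:1 and 1:3 (4.1); 500 cases (7.1); hospitalised share 35% without HIV (7.1) and 436/1,187 = 36.7% with HIV (6.1). The two shares are proxies only: they come from different populations, and at least the second counts hospitalisation at any time.

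**Assumed inputs.** 25% of HIV-negative patients are inpatients at diagnosis. Composite risk (inpatient/outpatient) is 0.40/0.04, 0.35/0.02 or 0.30/0.05, the same with and without HIV.

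**Step 1: setting mix among controls.** With inpatient share f among cases, the share among controls is g = f / [f + 3(1 − f)].

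- f = 25%: 125 + 3 × 375 = 1,250 controls, of whom 125 (10%) are inpatients.
- f = 36.7%: 183.7 + 3 × 316.3 ≈ 1,133 controls, about 16% inpatients.

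**Step 2: pooled model, no HIV effect of any kind.** p = share × inpatient risk + (1 − share) × outpatient risk, and HR = ln(1 − p_cases)/ln(1 − p_controls), with f = 25% and g = 10%.

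| Risk in/out | Cases | Controls | Pooled HR | HR within setting |
|---|---|---|---|---|
| 0.40/0.04 | 0.1300 | 0.0760 | 1.76 | 1.00 |
| 0.35/0.02 | 0.1025 | 0.0530 | 1.99 | 1.00 |
| 0.30/0.05 | 0.1125 | 0.0750 | 1.53 | 1.00 |

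A small Cox simulation agrees (40 replicates per scenario, no HIV effect, 30-37% inpatient, risks 0.30-0.40 and 0.05). The unstratified HR was about 1.6-1.8, with p < 0.05 in 88-100% of replicates. The stratified HR was 0.99-1.07. None of these figures is adjusted for the covariates in 7.3.2, which could absorb part of the distortion.

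**Step 3: size of the lost pathway.** Suppose HIV raises the inpatient share from 25% to 30% (×1.2) or 37.5% (×1.5) and does nothing afterwards. The total HR compares cases with an unmatched HIV-negative group at 25%. The last column uses 35% against 36.7%.

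| Risk in/out | Total HR, ×1.2 | Total HR, ×1.5 | Total HR, plan's proxies |
|---|---|---|---|
| 0.40/0.04 | 1.15 | 1.38 | 1.04 |
| 0.35/0.02 | 1.17 | 1.44 | 1.05 |
| 0.30/0.05 | 1.12 | 1.30 | 1.03 |

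The HR within matched setting is 1.00 in every cell. For the ×1.2 and ×1.5 scenarios, the pooled model would give 1.58-2.00.

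**Step 4: admission threshold.** Assume no HIV effect, but 5 percentage points of PLWHIV, with 15% risk, are admitted who would otherwise be outpatients (other inputs 25%, 0.40, 0.04).

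- Inpatients: (0.25 × 0.40 + 0.05 × 0.15)/0.30 = 0.358, against 0.40; ratio 0.90.
- Outpatients: (0.75 × 0.04 − 0.05 × 0.15)/0.70 = 0.032, against 0.04; ratio 0.80.
- Pooled model: cases 0.130, controls (0.30 × 0.40 + 2.1 × 0.04)/2.4 = 0.085; HR 1.57.

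Admission practice alone thus moves the within-setting estimates below 1 while the pooled estimate stays well above 1.

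**The case against.** The strongest defence is that the matching is deliberate and reasonable. It was added by amendment, and section 6.2 shows concern about how hospital-diagnosed controls are chosen. With controls drawn from sites or existing databases, an unmatched inpatient share could simply reflect the source, so dropping the match would not by itself yield a valid total effect. This stands, and it is why the matching should stay. It does not answer the point about interpretation: perfectly unbiased matching on setting still removes the pathway.

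It is also fair that objective 1 in section 3.1 is only to describe outcomes, and that 7.3 speaks of association. The impact wording in 7.3.2 remains unqualified.

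Other limits also stand. Setting at diagnosis is recorded separately from hospitalisation for COVID-19, and only the latter is an endpoint (3.4). Some inpatients may have tested positive while in hospital for another reason, and the documents do not separate them. So this variable is not purely a severity measure.

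A reader might infer that the primary HR omits every effect of HIV that brings people to hospital. The documents do not support that: status is fixed at diagnosis, and admission, critical care or death after an outpatient diagnosis is still observed. For the same reason the design only partly repeats the gap that section 2 notes in the UK cohort ("albeit with no data around the risk of developing severe COVID-19 or hospitalisation among this cohort in the first place"), which concerned people already hospitalised.

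**Conclusion.** The point holds in two parts. First, the matched sample cannot show an HIV effect that acts through inpatient status at diagnosis, so the primary result is at best conditional on setting, and the plan does not say so. This follows from the design and needs no assumed numbers. Second, the model as written does not give that conditional HR, because it ignores setting and matched set while the control ratio differs by setting.

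The sizes are illustrative. With 25% inpatient at diagnosis and risks of 30-40% and 2-5%, the pooled unadjusted HR is about 1.5-2.0 with no HIV effect, as large as the effects the study is powered to detect. The lost pathway is not quantified by the documents: a total HR of 1.12-1.44 needs an assumed 20-50% rise in inpatient diagnosis, and the plan's hospitalisation proxies suggest about 1.03-1.05.

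A reader might infer that the planned HR will sit near or below 1 and hide a harmful effect of HIV. That would apply only to a stratified or within-setting analysis. For the pooled model in 7.3.2 the likely error runs the other way.

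**What to change.** Keep the matching, and change the analysis and the wording:

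1. In 7.3.2, stratify the primary Cox model by matched set, or at least by inpatient or outpatient status at diagnosis. The distortion from the unequal ratios has to be removed; a caveat is not enough.
2. Report the HIV HR separately for inpatient-diagnosed and outpatient-diagnosed sets.
3. In 7.3 and 7.3.2, state the estimand as severity after diagnosis, given setting at diagnosis. State that it supports no conclusion, in either direction, about whether HIV raises the overall risk of severe COVID-19.
4. Name a different admission threshold for PLWHIV as a possible bias within each setting.

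Setting at diagnosis is already collected (6.2). Stratifying by matched set also needs the set identifier kept in the analysis data. The cost is protocol wording, a revised model statement and one table by setting. The downside is a narrower headline claim and wider intervals within each setting.
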